#### **2.1.4 Safety endpoints**

The safety analysis will be based on the reported adverse events (AEs) and other safety information, such as clinical laboratory data and vital signs.

##### ***Observation period***

For all enrolled patients, the period of safety observation starts from the time when the patient gives his/her informed consent and is divided into the following periods:

- The PRE-TREATMENT observation period is defined from the signed informed consent up to the first dose of alirocumab.
- The treatment-emergent adverse event (TEAE) period is defined as the time from the first injection of alirocumab up to the day of the last injection of alirocumab + 14 days.
- The POST-TREATMENT period will cover a period from the day after the end of the TEAE period up to the end of the study (defined as last protocol-planned visit or the resolution/stabilization of all SAEs and AEs with pre-specified monitoring as defined in protocol).

The on-study observation period is defined as the time from the day of first dose of alirocumab until the last protocol planned visit of the patient.

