#### **2.4.5 Analyses of safety data**

##### *General common rules*

All safety analyses will be performed on the Safety population using the following common rules:

- The baseline value will be defined as the last available value before the first alirocumab injection.
- The potentially clinically significant abnormality (PCSA) values are defined as abnormal values considered medically important by the Sponsor according to predefined criteria/thresholds based on literature review and defined by the Sponsor for clinical laboratory tests and vital signs (PCSA version dated May 2014, see [Appendix A](#)).
- PCSA criteria will determine which patients had at least 1 PCSA during the TEAE period, taking into account all evaluations performed during the TEAE period, including unscheduled or repeated evaluations. The number of all such patients will be the numerator for the PCSA percentages.

- The treatment-emergent PCSA denominator for a given parameter will be based on the number of patients assessed for that given parameter in the TEAE on the safety population.
- The worst on-treatment value is defined as the nadir and/or the peak value during the treatment period according to the direction (Min or Max) of the abnormality as defined the PCSA list. The last on-treatment value is defined as the last value collected during the treatment period.
- All measurements, scheduled or unscheduled, fasting or not fasting, will be assigned to analysis windows defined in [Section 2.5.4](#) in order to provide an assessment for all time points.

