#### **2.4.5.3 Analyses of laboratory variables**

The summary statistics (including mean, median, Q1, Q3, SE Min and Max) of some laboratory variables (absolute values and changes from baseline) will be calculated for each visit, last and worst value assessed during the treatment period. Since no central laboratory was used in this study, results obtained from local laboratories will be converted into the units listed in [Appendix A](#). For a given parameter, if no unit is indicated, no quantitative analysis will be performed.

The incidence of PCSA (list provided in [Appendix A](#)) at any time during the TEAE period will be summarized by biological function whatever the baseline level and/or according to the following baseline status categories:

- Normal/missing.
- Abnormal according to PCSA criterion or criteria.

For parameters for which no PCSA criteria are defined, similar table(s) using the normal range will be provided. A listing of patients with at least one post-baseline PCSA will be provided.

The absolute change in HbA1c (%) will be assessed from baseline to Weeks 12, 24, 48, 72, 96 and EOT/EOS.

For parameters HbA1c, FPG and LDL-C plots will be displayed; mean changes from baseline with the corresponding SE will be plotted over time (at same time points).

For the parameters assessed through dipstick urinalysis, no central laboratory was used. As a consequence, the results of statistical analyses on these parameters will have to be interpreted with caution.

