### ***Drug-induced liver injury***

The liver function tests, namely AST, ALT, alkaline phosphatase, and total bilirubin, are used to assess possible drug-induced liver toxicity. The proportion of patients with PCSA values or ALT increase as defined in AESI section (see [Section 2.1.4.1](#)) at any post-baseline visit by baseline status will be displayed for each parameter.

A graph of distribution of post-baseline peak values of ALT versus peak values of total bilirubin will also be presented. Note that the ALT and total bilirubin values are presented on a logarithmic scale. The graph will be divided into 4 quadrants with a vertical line corresponding to 3 x ULN for ALT and a horizontal line corresponding to 2 x ULN for total bilirubin.

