#### **2.4.5.4 Analyses of vital sign variables**

The summary statistics (including mean, median, Q1, Q3, SE, Min and Max) of all vital signs parameters (raw data and changes from baseline) will be calculated for each visit, last and worst value assessed during the treatment period.

Additionally, the incidence of PCSAs at any time during the TEAE period will be summarized irrespective of the baseline level and/or according to the following baseline status categories:

- Normal/missing.
- Abnormal according to PCSA criterion or criteria.

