#### **2.5.4 Windows for time points**

Data analyzed by time point (including efficacy, laboratory safety data, vital signs) will be summarized using the analysis windows given in [Table 3](#). These analysis windows will be applicable for all analyses, and they are defined to provide more homogeneous data for time point-specific analyses.

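### PCSA incidence tables close at last injection + 14 days, but the EOT/EOS visit runs from day 14 to day 21, so planned final values from days 15-21 are not counted

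*SAP*

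**What the plan says.** SAP 2.1.4 (Observation period) ends the TEAE period on day 14 after the last injection: "the time from the first injection of alirocumab up to the day of the last injection of alirocumab + 14 days".

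SAP 2.4.5 ties PCSA counting to that period. For the numerator: "PCSA criteria will determine which patients had at least 1 PCSA during the TEAE period". The denominator is "based on the number of patients assessed for that given parameter in the TEAE on the safety population". SAP 2.4.5.3 repeats the limit for laboratory PCSAs ("at any time during the TEAE period will be summarized by biological function") and SAP 2.4.5.4 for vital signs ("the incidence of PCSAs at any time during the TEAE period will be summarized irrespective of the baseline level").

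Protocol 10.1.2.5 places EOT/EOS at 14 days (+7) after the last injection, with vital signs, HbA1c and other laboratory tests.

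The protocol gives two ends for the TEAE period: +14 days in 9.1.1, and a range of +14 to 21 days in 11.4.2, the section that also states the PCSA rule. The SAP adopts +14, and neither SAP 1.5 nor 1.6 mentions the choice.

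Three SAP outputs are not tied to the TEAE period:
- the listing in 2.4.5.3: "A listing of patients with at least one post-baseline PCSA will be provided";
- the liver display, which covers PCSAs and the ALT increase "at any post-baseline visit by baseline status will be displayed for each parameter";
- the by-visit summaries: "Data analyzed by time point (including efficacy, laboratory safety data, vital signs) will be summarized using the analysis windows given in" Table 3.

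**The concern.** The visit window opens on the day the counting period closes. Whether a planned final assessment enters a primary-endpoint percentage then depends on whether the patient came on day 14 or day 15, which has nothing to do with safety. A PCSA first seen on day 18 is left out of the numerator, while a patient assessed earlier stays in the denominator. The same day-18 blood draw lies inside the efficacy treatment period, which SAP 2.3.1 runs to last injection + 21 days.

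The cut-off also reaches one adverse-event analysis. The ALT event of special interest is selected from laboratory data (SAP 2.1.4.1), and the Kaplan-Meier analysis of special-interest events censors event-free patients at the end of the TEAE period (SAP 2.4.5.1). An ALT rise first sampled on days 15-21 may be missed there yet appear in the liver display, so two outputs could give different counts for the same abnormality.

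**Working it through.** **Inputs.** TEAE end: last injection + 14 days, day 14 included (SAP 2.1.4). EOT/EOS: 14 days, +7 (Protocol 10.1.2.5). Anticipated sample: about 1300 (SAP 1.3).

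**Day count.** 14 + 7 = 21, which reproduces the protocol's 14-21 day window. Permitted days: 21 - 14 + 1 = 8. Inside the TEAE period: day 14 only, 1 of 8. Outside: days 15-21, 7 of 8 (87.5% of days). If counting ran to +21, 8 of 8 would be inside.

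**Direction.** Let n patients be assessed in the TEAE period, x of them with a PCSA. Let k of the n have their first PCSA on days 15-21. The table reports x/n; with the visit counted it would be (x + k)/n. The difference is k/n, never negative. A patient with no earlier in-period assessment of that parameter leaves both numerator and denominator, and the effect of that can go either way.

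**Size, by assumption only.** Let q be the proportion of patients whose first PCSA for a parameter is at EOT/EOS, and s the share of those visits on days 15-21. The understatement is q × s. The documents give neither value.

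| q | s | q × s (percentage points) | of 1300 patients |
|---|---|---|---|
| any | 0 | 0 | 0 |
| 0.5% | 25% | 0.125 | 1.6 |
| 1% | 50% | 0.5 | 6.5 |
| 2% | 100% | 2.0 | 26 |

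**Which parameters.** Vital signs and HbA1c are planned at EOT/EOS and have criteria in SAP Appendix A. For hematology and chemistry the protocol conflicts: the Laboratory tests list in Section 10 excepts EOT/EOS, while Protocol 10.1.2.5 and SAP 2.1.4.3 include it.

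**Where a day-15 to day-21 value still appears.**
- PCSA listing: yes, but it gives no incidence.
- Liver display: yes, for AST, ALT, alkaline phosphatase and total bilirubin only.
- By-visit summaries: only if the study day falls in a Table 3 window. The gaps after Week 12 are Days 99-154 (56 days), 183-238 (56), 267-315 (49), and six of 42 days each (358-399, 442-483, 526-567, 610-651, 694-735, 778-819). Total: 56 + 56 + 49 + 6 × 42 = 413 of the 777 days from Day 85 to Day 861. Patients may switch at any time after 12 weeks (Protocol 6.2.1), so an exit can fall in a gap.
- EOT/EOS HbA1c change (SAP 2.4.5.3): planned, but Table 3 has no EOT/EOS row. SAP 2.1.3.2 labels Week 120 as EOT/EOS, although patients may leave much earlier.
- Last and worst on-treatment values: unclear. SAP 2.4.5 refers to a treatment period whose end it does not state there, and SAP 2.5.1 defines the last value differently, as at or just before the last study drug intake.

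**The case against.** The +14 cut-off has support. It follows Protocol 9.1.1, equals one dosing interval and matches the exposure formula in SAP 2.4.3.1. A visit held on its nominal day 14 is counted; days 15-21 are allowance. The study is single-arm and descriptive, so no treatment comparison is biased. Unscheduled evaluations within the period count, and premature discontinuers should, if possible, have an EOT-type visit within 5 days (Protocol 10.3.2.2). All of this stands, and it is why +14 may remain the adverse-event cut-off.

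It can also be argued that later values do not belong in a treatment-emergent table. Total cholesterol and triglycerides are PCSA parameters in Appendix A, and Protocol Section 4 reports that the effect was not fully maintained over 4-week dosing intervals in earlier studies. Some late values may therefore reflect waning drug effect, and others a switch to commercial product or another lipid therapy. This stands as a reason to show both versions. It does not justify leaving the planned final assessment out of every PCSA percentage outside the liver display.

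The 21-day limit is not uniform either. Protocol 10.1.2.5 states it, and the flow chart's +7 agrees, but Protocol 6.1 and 10.3.2.2 and SAP 1.1 give only a minimum. A bare +21 rule could still drop later visits.

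**Conclusion.** The point holds for the PCSA incidence tables and for the time-to-event analysis of the laboratory-selected ALT event. As written, the SAP leaves on-schedule vital signs and HbA1c from days 15-21 out of the incidence tables. Hematology and chemistry are affected as well if the protocol conflict is resolved in favour of testing at that visit. The size is undocumented: 7 of 8 permitted days, an unknown share of patients, and zero if all visits are on day 14. The 0.125 to 2.0 point range rests wholly on the assumed q and s.

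A reader might infer more than the documents support:
- That end-of-treatment safety data are lost. They are not: the listing has no TEAE limit, nor does the liver display.
- That seven-eighths of final visits are excluded. That figure counts days, not patients.
- That adverse-event reporting in general is affected. Events are classified by when they developed, worsened or became serious, not by the visit date; the specific exposure is the ALT event.
- That every patient is affected. Those who left under the protocol before its global amendment had separate EOT and EOS visits (SAP 1.1), so this day count does not apply to them.

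This should be fixed before programming, because it decides what a primary-endpoint percentage counts.

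**What to change.** 1. Reconcile Protocol 9.1.1, Protocol 11.4.2 and SAP 2.1.4 into one stated adverse-event cut-off.
2. In SAP 2.4.5, present PCSA incidence in two versions, each with its own numerator and denominator: restricted to last injection + 14 days, and including the scheduled EOT/EOS assessment. Identify that assessment by visit, normally up to + 21 days. Flag values taken after a switch to commercial product or another lipid therapy, and also show the incidence without them. Apply the same rule to the laboratory-selected ALT event.
3. Keep one definition of the last on-treatment value (SAP 2.4.5 or 2.5.1) and state when the treatment period ends for last and worst values.
4. Add an EOT/EOS row to Table 3 defined relative to the last injection, as the 10-week follow-up row already is. Report it separately from the study-day rows and from Week 120, with a stated rule for overlap and for the early EOT-type visit of premature discontinuers.

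The passages on hematology and chemistry at EOT/EOS (Protocol Section 10, Protocol 10.1.2.5, SAP 2.1.4.3) must be reconciled before item 2 is programmed.

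**Cost.** SAP wording, one derivation run with and without the visit, one table row and short protocol clarifications. No new data; adverse-event periods and patient-year rates need not change if +14 is kept. If it is, one abnormality on days 15-21 could be both a counted PCSA and a post-treatment adverse event, and a footnote should say so. The wider version will include some values up to a week past the dosing interval, so the two versions should be read together.

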##### ***2.1.4.1 Adverse events variables***

Adverse events, including AESIs, SAEs and product complaints, will be collected from the time the patient signs the informed consent to the completion of the safety observation period. All AEs diagnosed by the investigator will be reported and described.

All AEs will be coded to a “lowest level term (LLT)”, “preferred term” (PT), “high level term (HLT)”, “high level group term (HLGT)” and associated primary “system organ class (SOC)” using the version of MedDRA currently in effect at Sanofi at the time of the considered database lock.

##### ***Adverse event observation period***

- Pre-treatment adverse events are AEs that developed or worsened or became serious during the pre-treatment period.
- Treatment-emergent adverse events are AEs that developed or worsened or became serious during the TEAE period.
- Post-treatment adverse events are AEs that developed or worsened or became serious during the post-treatment period.

### ***Adverse events of special interest***

An AESI is an AE (serious or non-serious) that needs to be monitored, documented, and managed in a pre-specified manner described in the protocol.

Following an amendment to the initial protocol (See [Section 1.5](#)), the AESIs will be analyzed according to the amended protocol.

For this study, the AESIs are the following:

- Increase in alanine aminotransferase (ALT): ALT  $\geq 3 \times$  upper limit of normal range (ULN) (if baseline ALT  $<$ ULN) or ALT  $\geq 2$  times the baseline value (if baseline ALT  $\geq$ ULN), selected using laboratory data (see Appendix F in the protocol).
- **Allergic events that require consultation with another physician** will be described. Events will be selected using the following standardized MedDRA query (SMQ): “hypersensitivity” (broad and narrow) excluding the preferred terms linked to local injection site reactions (“infusion site dermatitis”, “infusion site hypersensitivity”, “infusion site rash”, “injection site dermatitis”, “injection site hypersensitivity”, and “injection site rash”). The condition “consultation with another physician” will be considered as verified if a dermatology consultation was completed and/or if a description of the rash was provided by the dermatology consultation.
- In addition, an analysis will be performed for any allergic event whether meeting or not AESI criteria meeting the above SMQ criteria.
- **Local injection site reactions that are allergic in nature** deemed to be allergic by the Investigator (or have an allergic component) AND that require consultation with another physician will be selected using the PTs corresponding to local allergic reactions: “Injection site dermatitis”, “Injection site hypersensitivity”, “Injection site oedema”, “Injection site rash”, “Injection site urticaria”, “Injection site eczema”, “Injection site vasculitis”, “Injection site swelling”, “Infusion site dermatitis”, “Infusion site hypersensitivity”, “Infusion site oedema”, “Infusion site rash”, “Infusion site urticaria”, “Infusion site swelling”. The condition “consultation with another physician” will be considered as verified if a dermatology consultation was completed and/or if a description of the rash was provided by the dermatology consultation.
- An analysis using these PTs will also be performed for any local injection site reaction whether requiring consultation or not.
- In addition, an analysis will be performed for any local injection site reaction not meeting AESI criteria (not allergic and not requiring consultation with another physician) using the HLT “injection site reaction”.
- **Pregnancy** of female patients will be selected using the appropriate MedDRA codes.

- **Symptomatic overdose with Alirocumab.** Overdose with alirocumab is defined as at least twice of the intended dose within the intended therapeutic interval (ie, 2 or more injections are administered in <7 calendar days), to be reported using the Term “symptomatic OVERDOSE” (accidental or intentional), indicating the circumstance in parentheses (eg, “symptomatic overdose [accidental]” or “symptomatic overdose [intentional]”). These events will be selected using the AESI category as selected by the site.
- Another analysis will be performed using all overdose cases (whether symptomatic or asymptomatic and whether with alirocumab or another drug) using the HLT “Overdose”.
- In addition, an analysis will be performed using all overdose cases (whether symptomatic or asymptomatic) using the HLT “Overdose” with the condition “relationship to investigational medicinal product (IMP)” as YES.
- **Neurologic events that require additional examinations/procedures and/or referral to a specialist** will be selected using SMQ “demyelination” (broad and narrow), “peripheral neuropathy” (broad and narrow), and “Guillain Barre syndrome” (broad and narrow) excluding the following preferred terms: “acute respiratory distress syndrome”, “asthenia”, “respiratory arrest”, and “respiratory failure”.
- An additional analysis will be performed analyzing all events meeting the above SMQ criteria for neurologic events whether or not the criteria for an AESI are met (whether or not requiring additional exams/procedures and/or referral to a specialist).
- **Neurocognitive events** will be selected using the sponsor Company MedDRA Query (CMQ) based on HLTs “Deliria (incl confusion)”, “Cognitive and attention disorders and disturbances”, “Dementia and amnestic conditions”, “Disturbances in thinking and perception”, “Mental impairment disorders”.
- In a second approach, neurocognitive events will be analyzed using the CMQ developed using the Food and Drug Administration (FDA) grouping of events based on PTs “Amnesia”, “Amnestic disorder”, “Anterograde Amnesia”, “Neuropsychiatric symptoms”, “Change in sustained attention”, “Cognitive Disorder”, “Confusional State”, “Delirium”, “Dementia”, “Dementia Alzheimer's type”, “Dementia with Lewy Bodies”, “Disorientation”, “Disturbance in attention”, “Executive dysfunction”, “Frontotemporal Dementia”, “Illogical Thinking”, “Impaired reasoning”, “Incoherent”, “Judgement impaired”, “Memory Impairment”, “Mental Impairment”, “Mental Status Changes”, “Mini Mental Status Examination Abnormal”, “Presenile Dementia”, “Retrograde Amnesia”, “Senile Dementia”, “Thinking Abnormal”, “Transient Global Amnesia”, “Vascular Dementia” and the LLTs “Mental State Abnormal Aggravated”, “Thinking Slowed”.

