#### **10.4.1.3 Adverse event of special interest**

An adverse event of special interest (AESI) is an AE (serious or non-serious) that needs to be monitored, documented, and managed in a pre-specified manner described in the protocol.

For this study, the AESIs are the following (refer also to [Section 10.4.4](#) for the reporting time frame, and the corresponding complementary forms in the e-CRF to be filled):

- **Increase in alanine aminotransferase (ALT):**
  - ALT  $\geq 3 \times$  ULN (if baseline ALT  $<$ ULN) or ALT  $\geq 2$  times the baseline value (if baseline ALT  $\geq$ ULN) (Please refer to related flowchart in [Appendix F](#)).
- **Allergic events that require consultation with another physician** for further evaluation of hypersensitivity/allergy as per the Investigator's medical judgment.
- **Local injection site reactions that are allergic in nature:**
  - Local injection site reactions deemed to be allergic by the Investigator (or have an allergic component) and that require consultation with another physician for further evaluation of hypersensitivity/allergy as per the Investigator's medical judgment should be reported as AESIs.

Note: Other local injection site reactions are non-AESIs. Please see [Section 10.4.1.4](#) for details.

Note: The safety instructions on allergic events and local injection site reactions are detailed in [Section 10.6](#).
- **Pregnancy:**
  - Pregnancy occurring in a female patient or the female partner of a male patient (if data collection is permitted by the female partner and by local regulatory authorities) during the study or within 70 days (10 weeks) following the last dose of IMP.
  - Pregnancy will be recorded as AESI in all cases. Pregnancy will be qualified as an SAE only if it fulfils one or more SAE criteria.
  - In the event of pregnancy of a female patient included in the study, the IMP should be permanently discontinued.
  - The follow-up of the pregnancy will be mandatory until the outcome is determined.
- **Symptomatic overdose with IMP:**

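### The SAP's exclusion from the general allergic AESI leaves out eight of its own fourteen local injection-site terms, so any of the eight that the hypersensitivity SMQ contains at database lock would fall into both allergic categories

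*SAP*

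**What the plan says.** SAP section 2.1.4.1, under adverse events of special interest, defines two allergic categories.

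- **General allergic events that need a consultation.** These are selected by the hypersensitivity SMQ, broad and narrow, "excluding the preferred terms linked to local injection site reactions". The bracket that follows names six PTs: "infusion site dermatitis”, “infusion site hypersensitivity”, “infusion site rash”, “injection site dermatitis”, “injection site hypersensitivity”, and “injection site rash".
- **Local injection site reactions that are allergic in nature and need a consultation.** These "will be selected using the PTs corresponding to local allergic reactions", and fourteen PTs follow. Besides the dermatitis and hypersensitivity terms for each site, the injection-site part runs "Injection site oedema”, “Injection site rash”, “Injection site urticaria”, “Injection site eczema”, “Injection site vasculitis”, “Injection site swelling" and the infusion-site part runs "Infusion site oedema”, “Infusion site rash”, “Infusion site urticaria”, “Infusion site swelling".

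In both categories the consultation condition "will be considered as verified if a dermatology consultation was completed", or if the dermatology consultation supplied a description of the rash. A supplementary analysis repeats the general selection for any allergic event, without that condition. Another repeats the local PT list whether or not a consultation was needed.

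SAP section 2.4.5.1 tabulates each AESI by these selections, by SOC and PT, and provides Kaplan-Meier curves for all AESIs when appropriate. MedDRA coding uses the version in effect at the time of database lock (SAP 2.1.4.1). Protocol section 10.4.1.3 gives local allergic reactions a bullet of their own: "Local injection site reactions deemed to be allergic by the Investigator (or have an allergic component") and needing a consultation.

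**The concern.** The stated purpose of the exclusion is to keep local injection-site terms out of the general allergic set. The terms named do not cover what the SAP itself, a few lines later, classes as local allergic reactions. Nothing else in the section separates the two sets: the consultation condition is the same for both, and no rule says where an event goes if it meets both selections.

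Safety is the primary endpoint. Protocol section 4 describes injection site reactions as an identified adverse reaction to the drug, and allergic reactions as rare and sometimes serious. With a rare category and no control arm, even a few purely local events could shift the reported general allergic rate noticeably.

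There is also an asymmetry. The local AESI requires that the investigator consider the reaction allergic; the general selection does not. A local reaction that the investigator judged non-allergic could therefore enter an allergic table through its PT alone. Protocol section 10.6.2 treats events that are plainly not allergic as belonging on the local form only.

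**Working it through.** The plan gives no figure to reproduce on this point. The check is a comparison of the two PT lists in SAP 2.1.4.1.

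| Term | Injection site: on local list | Injection site: excluded from SMQ | Infusion site: on local list | Infusion site: excluded from SMQ |
|---|---|---|---|---|
| dermatitis | yes | yes | yes | yes |
| hypersensitivity | yes | yes | yes | yes |
| rash | yes | yes | yes | yes |
| oedema | yes | no | yes | no |
| urticaria | yes | no | yes | no |
| swelling | yes | no | yes | no |
| eczema | yes | no | – | – |
| vasculitis | yes | no | – | – |

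1. Local list: 8 injection-site + 6 infusion-site = 14 PTs, all distinct.
2. Exclusion list: 3 + 3 = 6 PTs, all of them among the 14.
3. Local but not excluded: 14 − 6 = 8 PTs, of which 5 are injection-site and 3 infusion-site.
4. A PT enters the general set only if it is in the SMQ and not excluded. Let k be the number of the eight that the SMQ contains at lock. Then k PTs are selected in both categories, with 0 ≤ k ≤ 8. Alirocumab and the training placebo are given only by subcutaneous injection (Protocol 8.1), so the three infusion-site terms are unlikely to be used, and the practical range is 0 to 5.
5. Extra patients in the general allergic count = patients whose only SMQ-selected event is coded to one of those k PTs. For the AESI itself they must also meet the consultation condition; for the analysis of any allergic event they need not. The documents give neither k nor any event frequency by PT, so this number cannot be calculated. Its lower limit is zero.
6. With all 14 PTs excluded, the overlap between the two PT selections is zero for every k.

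**The case against.** The two lists do different jobs. A selection list must name every term wanted; an exclusion list need only name the local terms that the SMQ contains. Six exclusions beside fourteen selections is just what one would see if the SMQ held only those six when the SAP was written. Neither document shows otherwise.

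Nor does the protocol require strictly separate categories. Section 9.1.1 puts both in one bullet and Appendix E in one row. Section 10.6.2 gives swelling at the injection site as an example of a possible allergic reaction. Section 10.6.1 and Appendix E call for both the local and the general parts of the form when a local reaction progresses. The AESI tables are by PT, so a stray injection-site term would be visible under its own name. All analyses are descriptive.

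Much of this stands. It makes the consequence conditional, and it limits the effect on the AESI table, where a dermatology consultation is needed and each PT is shown. It does not close the gap. The SAP does not say that the six are complete for the SMQ, and it fixes the list while letting the MedDRA version run to database lock, so a list complete at writing may be incomplete at analysis. A programmer who finds another local PT in the SMQ cannot tell whether the description or the bracket governs. The overlap that the protocol foresees depends on progression, whereas the SAP selects by PT. A Kaplan-Meier curve of time to first event does not show which PT produced each event.

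**Conclusion.** The mismatch is established: the exclusion omits 8 of the 14 PTs that the SAP classes as local allergic reactions, and no other rule keeps them out of the general selection. The consequence is conditional on the SMQ version in force at lock. Between 0 and 8 PTs (0 to 5 if infusion-site terms are not used) would be selected in both the general and the local category. The general allergic AESI, its Kaplan-Meier curve and, with the least protection, the analysis of any allergic event could then include purely local reactions.

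A reader might infer more: that injection site urticaria and similar terms will be reported as systemic reactions, that the general rate will be overstated by a known fraction, or that events will be counted twice in a total. The documents support none of these. They do not list the SMQ's terms; the SAP speaks of allergic events, not systemic ones; any percentage would be one assumed rate divided by another; and no total pooled across AESIs is planned. What remains is possible overlap between two separately reported categories and possible inflation of one of them, of a size that cannot be computed here.

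**What to change.** In SAP 2.1.4.1, extend the bracketed exclusion from the hypersensitivity SMQ to all fourteen PTs on the SAP's local list, or to every injection-site and infusion-site PT in the SMQ version used at database lock. State that the same exclusion applies to the analysis of any allergic event. A local reaction that progresses would still count as a general allergic event where its general component is coded to its own PT in the SMQ.

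If the sponsor prefers to keep the six terms, the alternative is to state which of the other eight are in the SMQ version used, and how an event that meets both selections is reported.

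The cost is one edited list and the matching line of programming. No data collection changes. Excluding a PT that the SMQ does not contain has no effect, so the change does no harm if the concern turns out to be empty.
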